**Table 4-2: Schedule of Assessments –Treatment Phase (T17 – T48)**

Procedure/Assessments	Treatment Phase (T17 – T48)											In case of Treatment Failure	
	Visit	T17	T18-21	T22-25	T26-29	T30-33	T34-37	T38-41	T42-45	T46	T47		T48
Window Period	±3 days since last treatment												
Physical Examination	X 	X 	X 	X 	X 	X 	X 	X 	X 	X 	X 	X	X
Neurological Assessment 												X	X
Vital Signs 	X	X	X	X	X	X	X	X	X	X	X	X	X
ECG												X	X
Complete Blood Count (CBC) 			X				X					X	X
Biochemistry 			X				X					X	X
Coagulation Indices			X				X					X	X
Urinalysis			X				X					X	X
Plasma HIV-1 RNA level 	X	X	X	X	X	X	X	X	X			X	X
TruCount T assay 	X	X	X	X	X	X	X	X	X			X	X
Trofile® DNA Assay												X	X 
Trofile® RNA Assay													X 
HIV-1 Drug Resistance Assay 												X	X
PRO 140 Administration – Group A (350mg SC) – Group B (525mg SC) – Group C (700mg SC)	X	X	X	X	X	X	X	X	X	X	X	X	
Combination ART Regimen 											X	X	X
Injection Site Reaction Assessment 	X	X	X	X	X	X	X	X	X	X	X	X	
Injection Site Pain Assessment (VAS) 	X	X	X	X	X	X	X	X	X	X	X	X	
PK sample for PRO 140 		X		X			X		X			X	X
Anti-idiotypic antibodies to PRO 140 		X		X			X		X			X	X
Measurement of treatment adherence 		X	X	X	X	X	X	X	X	X	X	X	X
Adverse Events	X	X	X	X	X	X	X	X	X	X	X	X	X
Concomitant Medications	X	X	X	X	X	X	X	X	X	X	X	X	X
Potential Biomarkers													
Immune Activation Markers 												X	X
PhenoSense® Entry Assay 												X	X
Quest Diagnostics Tropism Assay 													X

Procedure/Assessments	Treatment Phase (T17 – T48)											In case of Treatment Failure
	Visit	T17	T18-21	T22-25	T26-29	T30-33	T34-37	T38-41	T42-45	T46	T47	
Window Period	±3 days since last treatment											
CNS sub-study (n=20)												
CSF sample collection 												X
GU sub-study (n=20)												
Genital Secretion sample collection 												X
CCR5 Receptor Occupancy 	X	X	X	X	X	X	X	X	X	X	X	X
CCR5 Genotyping 											X	X

**Foot Notes:**

- [1] Symptom-directed physical examination at clinic visits.
- [2] The neurological assessment tool is based on the three question survey used by Simioni et al. (Simioni S, 2010). Additional neurological assessment modalities may be used as per Investigator's discretion.
- [3] Post treatment vital signs (blood pressure, heart rate, respiration rate, and temperature) will be measured at clinic visit.
- [4] Hemoglobin, Hematocrit (HCT), Red Blood Cells (RBC), White Blood Cells (WBC) with total and differential count, Absolute Neutrophil Count (ANC) and platelets.
- [5] Serum Biochemistry  
 Hepatic function indicators: total and direct bilirubin, alkaline phosphatase, aspartate aminotransferase (AST), alanine aminotransferase (ALT), total protein, Lactate dehydrogenase (LDH)  
 Renal function indicators: BUN, creatinine  
 Electrolytes: sodium, potassium, chloride, calcium and bicarbonate  
 Other: glucose (random), cholesterol (total)
- [6] Blood sample for plasma HIV-1 RNA level collected at least once every four weeks between T18-21, T22-25, T26-29, T30-33, T34-37, T38-41 and T42-45 visits when subject comes to clinic.
- [7] Blood sample for TruCount T assay collected at least once every four weeks between T18-21, T22-25, T26-29, T30-33, T34-37, T38-41 and T42-45 visits when subject comes to clinic. Assay includes: Absolute Lymphocytes, CD3 cell count, CD4 cell count, CD8 cell count, CD3%, CD4% and CD8%
- [8] Monogram Biosciences GenoSure Archive Assay will be performed at T48 visit. PhenoSense® GT (and PhenoSense Integrase and GeneSeq Integrase testing, if applicable), will be performed at the time of virologic failure.
- [9] Study subjects will re-initiate their previous antiretroviral regimen or an alternative regimen selected by their treating physician: (1) One week prior to the end of 48-week Treatment Phase, or (2) Anytime during the Treatment Extension Phase, if virologic failure occurs or have met any other criteria for discontinuation of study treatment as specified in the protocol.
- [10] Injection Site Reaction Assessment as assessed by Investigator (or designee) at the clinic visits and by visiting nurse or qualified medical professional during home visits. Injection Site Reaction Assessment will not be applicable if PRO 140 is self-administered by subjects at home.
- [11] Subject-perceived injection site pain will be assessed using the Pain Visual Analog Scale (VAS) prior to study treatment administration which evaluates average pain since last treatment. Injection Site Pain Assessment will not be applicable if PRO 140 is self-administered by subjects at home.
- [12] Blood sample collected at anytime between T18-21, T26-29, T34-37 and T42-45 visits followed by at T48 and VF visits.
- [13] Treatment adherence self-reported by subject at least once every four weeks between T18-21, T22-25, T26-29, T30-33, T34-37, T38-41 and T42-45 visits followed by at T48 and VF visits when subject comes to clinic
- [14] immune activation markers (CRP, IL-6, D-Dimer)

- [15] Monogram Biosciences HIV-1 PhenoSense® Entry assay with AMD3100 (X4 inhibitor drug), Maraviroc and PRO 140 (R5 inhibitor drugs). Sample collected for Trofile DNA/RNA at Screening will be used to test PhenoSense® Entry for eligible/enrolled subjects at Baseline.
- [16] Quest Diagnostics HIV-1 Coreceptor Tropism with Reflex to Ultradeep Sequencing or HIV-1 Proviral Tropism.
- [17] To evaluate PRO 140 concentration and HIV-1 RNA level in cerebrospinal fluid (CSF)
- [18] To evaluate PRO 140 concentration and HIV-1 RNA level in genital secretions
- [19] Monogram Biosciences Trofile® DNA or RNA assay (or both) will be performed at the Virologic Failure Visit depending on the last known HIV-1 RNA levels
- [20] Should VF occur, Group A or Group B subjects may transition to high dose IP and continue in 48-week Treatment Phase
- [21] To assess the number CCR5 receptors on patients' CD4 cell surface, and number and percentage of CCR5 receptors that are covered by PRO 140. Sites should not collect samples on Fridays, since InCellDx lab cannot receive samples on Saturdays.
- [22] No new sample collection needed. The residual whole blood sample collected for tropism assessment at Screening or at post-treatment visits will be used for testing of CCR5 genotyping (homozygous or heterozygous status).

**Table 4-3: Schedule of Assessments –Follow-Up (FU) Phase**

## (a) Subjects who do NOT experience Virologic Failure

Procedure/Assessments	Follow-Up Visit -1	Follow-Up Visit -2
	NVF-FU1	NVF-FU2
Window Period	2 weeks (±3 days) after T48	4 weeks (±3 days) after T48
Physical Examination	X 	X 
Vital Signs	X	X
Plasma HIV-1 RNA level	X	X
TruCount T assay	X	X
Anti-idiotypic Antibodies to PRO 140		X
Re-initiate combination Antiretroviral Therapy	X	X
Adverse Events	X	X
Concomitant Medications	X	X

[1] Symptom-directed physical examination

## (b) Subjects who experience Virologic Failure

## • Short-Term Follow-Up Visits

Procedure/Assessments	Follow-Up Visit -1	Follow-Up Visit -2	Follow-Up Visit -3 
	VF-FU1	VF-FU2	VF-FU3
Window Period	4 weeks (±7 days) after VF visit	8 weeks (±7 days) after VF visit	12 weeks (±7 days) after VF visit
Physical Examination	X 	X 	X 
Vital Signs	X	X	X
Plasma HIV-1 RNA level	X	X	X
TruCount T assay	X	X	X
Anti-idiotypic Antibodies to PRO 140	X		
Re-initiate combination Antiretroviral Therapy	X	X	X
Adverse Events	X	X	X
Concomitant Medications	X	X	X

[1] Subject will be followed up every 4 weeks until viral suppression is achieved (i.e., plasma HIV-1 RNA levels decline to < 50 copies/mL). Subject will undergo additional follow-up visits every 4 weeks beyond VF-FU3 visit (up to a maximum of 6 months after re-initiation of combination antiviral therapy), if viral suppression is not achieved at the end of VF-FU3 visit.

[2] Symptom-directed physical examination

- Long-Term Follow-Up Visits

Procedure/Assessments	Long-Term Follow-Up Visit -1	Long-Term Follow-Up Visit -2
	VF-6mFU	VF-12mFU
Window Period	6 months ( $\pm 1$ month) after VF visit	12 months ( $\pm 1$ month) after VF visit
Adverse Events 	X	X
Assessment of cART changes 	X	X
Plasma HIV-1 RNA level	X	X
TruCount T assay	X	X
Trofile ® DNA or RNA Assay 	X	X
PhenoSense ® Entry Assay 	X	X
HIV-1 Drug Resistance Assay 	X	X

[1] Only SAEs and any AE that is considered possibly or probably or definitely related to the IP by the investigator will be captured during the long term follow up phase.

[2] Any changes to the combination antiretroviral regimen since the viral re-suppression is achieved.

[3] Monogram Biosciences Trofile® DNA or RNA (or both) assay will be performed depending on last known HIV-1 RNA levels.

[4] Monogram Biosciences HIV-1 PhenoSense® Entry assay with AMD3100 (X4 inhibitor drug), Maraviroc and PRO 140 (R5 inhibitor drugs).

[5] Monogram Biosciences GenoSure Archive Assay or PhenoSense® GT (and PhenoSense Integrase and GeneSeq Integrase testing, if applicable), will be performed depending on last known HIV-RNA levels.

## 4.1 SCREENING PHASE

### 4.1.1 Pre-Screening

Sites are encouraged to pre-screen subjects for study inclusion, evaluating HIV-1 DNA viral tropism prior to performing a full screening visit. Up to 15 clinical sites will be allowed to participate in this process.

The subject will sign and date the pre-screening informed consent form (ICF) prior to any study-related pre-screening procedures. A unique identification number (pre-screening number) will be assigned to each subject who has provided written pre-screening informed consent. The pre-screening number will incorporate a three-digit Study Center number (PS301, PS302, PS303....) and a two-digit numeric ID assigned in successive order of consenting to pre-screening procedures after signing the pre-screening ICF at each center, beginning with 001 at each site (e.g. PS301-01 or PS302-01).

Once the pre-screening ICF has been signed, the following procedures and information will be obtained to confirm pre-eligibility including:

- Review of prior medical records
- Blood sample collection for HIV-1 Co-receptor tropism analysis by Monogram Biosciences

A pre-screening log will be maintained to capture the following information:

- Pre-screening number
- Patient initials
- Date pre-screened
- Initial eligibility
- Date of re-consent (for the full consent form) or reason for ineligibility

### 4.1.2 Screening Visit

The subject (or Legally Acceptable Representative (LAR)) will sign and date the informed consent form (ICF) and Health Insurance Portability Accountability Act (HIPAA) authorization (according to site policy and practices) prior to any study-related procedures. A unique identification number (screening number) will be assigned to each subject who has provided written informed consent.

**Note:** *Screening numbers are independent of pre-screening number, if pre-screening performed.*

The subject screening number will incorporate a three-digit Study Center number (301, 302,

303....) and a three-digit numeric ID assigned in successive order of entering the study after signing the ICF at each center, beginning with 001 at each site (e.g. 301-001 or 302-001).

**Subject Screening # :**

**XXX - YYY**

XXX=Study Center

YYY=Subject Numeric ID

All study centers will be instructed to maintain the study-specific pre-screening, screening and enrollment logs at their sites. If a subject initially fails to meet inclusion/exclusion criteria and is later reconsidered for participation, the subject will be re-consented and assigned a new screening number at the time of re-screening. Subjects who fail their first screening attempt may be re-screened a maximum of once and may be enrolled if they are found to meet all inclusion and no exclusion criteria when re-screened.

Once the ICF has been signed, screening procedures and information will be obtained to confirm subject eligibility including:

- Detailed medical history (see [Section 7.4](#)),
- Demographic information (see [Section 7.3](#)),
- Prior and current medications review (see [Section 7.5](#)),
- Physical examination (see [Section 7.6](#)),
- Electrocardiogram (ECG) (see [Section 7.7](#)),
- Body Weight & Height measurements (see [Section 7.9](#))
- Vital Signs (see [Section 7.9](#)),
- Collection of Blood Specimens (see [Section 7.10](#)) for
  - Complete Blood Count
  - Biochemistry
  - Coagulation Indices [Prothrombin time (PT) and INR]
  - Hepatitis B surface antigen (HBsAg)
  - Plasma HIV-1 RNA level
  - TruCount T Assay
  - HIV-1 co-receptor tropism (Trofile® DNA Assay)
    - CCR5 Genotyping will be tested using residual whole blood sample from tropism sample collected at Screening
  - HIV-1 Drug Resistance Assay (GenoSure Archive Assay)

- HIV-1 PhenoSense® Entry (*Monogram BioSciences*)
- Serum pregnancy test, for female subjects of childbearing potential. Childbearing potential is defined as someone who is not surgically sterile or is not more than one year past complete cessation of menstrual cycles.
- Blood sample for evaluation of potential biomarkers
  - HIV-1 co-receptor tropism (Quest Diagnostics Proviral DNA® Assay)
- Collection of Urine Specimen for Urinalysis (see [Section 7.10.15](#))

All screening information will be fully documented in the subject's medical records (i.e., source documents).

- For consented subjects who do not meet eligibility criteria, a Screen Failure electronic Case Report Form (eCRF) will be completed. The Screen Failure eCRF will contain the following details: the subject identification number, the date of ICF signature, demographic information (see [Section 7.3](#)), and the reason for screen failure. No additional information will be required for subjects who fail screening.
- For consented subjects who meet eligibility criteria, all required screening information will be transcribed onto the appropriate page of the eCRF.

Eligible subjects that are not enrolled within 42 days of Screening Visit will have screening lab assessments repeated, with the exception of HIV-1 viral tropism, genotype and phenotype, to reconfirm eligibility.

## 4.2 TREATMENT PHASE

Treatment Phase begins with an evaluation of results of laboratory samples collected during the Screening Phase. Subjects who meet all eligibility criteria, as per data gathered from Screening Phase are to be treated. All subjects who fail to meet eligibility criteria will be considered screen failure and exit the study without further evaluation.

All subjects will continue their existing antiretroviral regimen for one week after receiving initial assigned dosing of PRO 140. Subjects will receive up to 48 weekly PRO 140 injections in the Treatment Phase, given once per week ( $\pm 3$  days) or until virologic failure, whichever occurs first. The study treatment (PRO 140 350mg or 525mg or 700mg SC injections) will be administered by a qualified medical professional (MD, DO, PA, LPN, LVN, NP, RN or CMA if permitted by state law) at clinic site or home visit or self-administered by subjects, for the duration of 48 weeks in the Treatment Phase.

As shown in [Table 4-4](#), eligible subjects will be randomized 1:1 to two treatment arms for 48 weeks.

**Table 4-4: Part 1: Randomized, Two-Arm, Open-Label Treatment Phase**

Study Drug	Dosage Form	IP concentration	Dosing Frequency and Amount	Route of Administration
GROUP A				
PRO 140 350mg	Parenteral solution	175 mg/mL	2 injections of PRO 140 (2 X 1 mL/inj.) for 48 weeks	SC injection
GROUP B				
PRO 140 525mg	Parenteral solution	175 mg/mL	2 injections of PRO 140 (2 X 1.5 mL/inj.) for 48 weeks	SC injection
GROUP C				
PRO 140 700mg	Parenteral solution	175 mg/mL	2 injections of PRO 140 (2 X 2 mL/inj.) for 48 weeks	SC injection

As shown in [Table 4-5](#), Group A subjects experiencing virologic failure (defined as two consecutive HIV-1 RNA levels of  $\geq 200$  copies/mL) in Part 1 of Treatment Phase will have option of reinitiating ART regimen or begin PRO 140 525mg SC weekly injections for remainder of 48-week Treatment Phase.

**Table 4-5: Part 2: Single-Arm, Open-label Treatment Phase [Group A]**

Study Drug	Dosage Form	IP concentration	Dosing Frequency and Amount	Route of Administration
PRO 140 525mg	Parenteral solution	175 mg/mL	2 injections of PRO 140 (2 X 1.5 mL/inj.) up to Week 48	SC injection

As shown in [Table 4-6](#), Group B subjects that elect to participate in Part 2 of Treatment Phase after experiencing virologic failure during Part 1 of Treatment Phase will receive PRO 140 700mg SC weekly injection for remainder of 48-week Treatment Phase. Should subject experience subsequent virologic failure in Part 2 of Treatment Phase, subject will complete Virologic Failure (VF) Visit assessments and then enter the Follow-up Phase of the study.

**Table 4-6: Part 2: Single-Arm, Open-label Treatment Phase [Group B]**

Study Drug	Dosage Form	IP concentration	Dosing Frequency and Amount	Route of Administration
PRO 140 700mg	Parenteral solution	175 mg/mL	2 injections of PRO 140 (2 X 2 mL/inj.) up to Week 48	SC injection

Group A or Group B subjects that do not elect to participate in Part 2 of Treatment Phase and all Group C subjects who experience virologic failure (defined as two consecutive HIV-1 RNA levels of  $\geq 200$  copies/mL) at any time during the Treatment Phase will undergo the Virologic

Failure (VF) Visit assessments and then exit the Treatment Phase to enter the Follow-up Phase of the study.

Subjects who do not experience virologic failure will enter the Follow-up Phase of the study at the end of 48-week Treatment Phase.

All study subjects will re-initiate their previous antiretroviral regimen or an alternative regimen selected by their treating physician:

- One week prior to the end of 48-week Treatment Phase, or
- Anytime during the Treatment Phase, if virologic failure occurs or have met any other criteria for discontinuation of study treatment as specified in [Section 5.2.1](#) of the protocol. Subjects will be allowed to continue PRO 140 monotherapy while waiting for new ART regimen to be constructed by the Investigator.

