### 3 STUDY DESIGN

This study is a Phase 2b/3, multi-center, randomized, two-part, open-label study designed to evaluate the efficacy, safety, and tolerability of the strategy of shifting clinically stable patients receiving suppressive combination antiretroviral therapy to PRO 140 monotherapy and maintaining viral suppression for 48 weeks following study entry.

Consenting patients will be shifted from combination antiretroviral regimen to weekly PRO 140 monotherapy for 48 weeks during Part 1 of Treatment Phase with the one week overlap of existing retroviral regimen and PRO 140 at the beginning of the study treatment and also one week overlap at the end of the treatment in subjects who do not experience virologic failure. The first ~150 eligible subjects were enrolled to receive PRO 140 350mg SC weekly injection in a single-arm study. Subsequently, next ~150 subjects were randomized 1:1 to PRO 140 350mg (Group A) or PRO 140 525mg (Group B). An additional ~200 subjects will be randomized 1:1 to PRO 140 525mg (Group B) or PRO 140 700mg (Group C).

As shown, subjects in Group A or Group B that experience virologic failure prior to week 48 in Part 1 have option of entering Part 2 wherein they receive higher dose of PRO 140 for remainder of treatment phase or may re-initiate prior ART regimen (or an alternative regimen selected by their treating physician) at the discretion of the subject and Investigator.

➤ **For the first ~150 enrolled subjects:**

- **Part 1:** 48-week, single-arm, open-label treatment phase
  - PRO 140 350mg SC weekly injection (Group A)

➤ **For the subsequent ~150 enrolled subjects:**

- **Part 1:** 48-week, randomized, two-arm, open-label treatment phase
  - PRO 140 350mg SC weekly injection (Group A)
  - PRO 140 525mg SC weekly injection (Group B)

➤ **For the subsequent ~200 enrolled subjects:**

- **Part 1:** 48-week, randomized, two-arm, open-label treatment phase
  - PRO 140 525mg SC weekly injection (Group B)
  - PRO 140 700mg SC weekly injection (Group C)

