**Note:**

- Subjects may return to clinic for an additional blood draw in-between the clinic visits for plasma HIV-1 RNA levels, per the discretion of the Investigator.
- Virologic failure is defined as two consecutive levels of  $\geq 200$  copies/mL.
  - Subjects in Group A that experience virologic failure have option of re-initiating ART regimen or participating in Part 2 of Treatment Phase and receive higher dose of PRO 140 (525mg SC) weekly injection for remainder of 48-week Treatment Phase or until subsequent virologic failure event after viral re-suppression on higher dose.
  - Subjects in Group B that experience virologic failure have option of re-initiating ART regimen or participating in Part 2 of Treatment Phase and receive higher dose of PRO 140 (700mg SC) weekly injection for remainder of 48-week Treatment Phase or until subsequent virologic failure event after viral re-suppression on higher dose.
- Subjects who meet any criteria (other than virologic failure) for discontinuation of study treatment as specified in [Section 5.2.1](#) of the protocol, will undergo T48 Visit assessments and enter the Follow-up Phase of the study.
- Subjects who do not experience virologic failure will enter the Follow-up Phase of the study at the end of 48-week Treatment Phase.

Visits during the Treatment Phase will commence on T1, i.e. the date of first treatment, with weekly visits ( $\pm 3$  days) thereafter. The first Treatment Visit (T1) will take place as soon as HIV-

1 viral tropism, genotype and phenotype resistance results are available for review by Investigator, within 6 weeks of the Screening Visit.

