**Note:** All treatment injections must be administered by a qualified medical professional (MD, DO, PA, LPN, LVN, NP, RN or CMA if permitted by state law) at clinic site or

home visit or self-administered by subjects, for the duration of 48 weeks in the Treatment Phase.

- Injection Site Reaction Assessment (see [Section 7.12](#))
  - **Note:** *To assess injection site reactions, the Investigator will use the DAIDS AE grading table (refer to [Section 17.3](#)).*
- Subject-perceived Injection Site Pain Assessment (see [Section 7.13](#))
  - **Note:** *Subject-perceived injection site pain will be assessed using the Pain Visual Analog Scale (VAS) prior to study treatment administration assessing average pain at injection site since last treatment.*
- Re-initiate previous antiretroviral regimen or an alternative regimen selected by the treating physician at Week-47, if viral load remain suppressed.

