#### 7.10.9 Plasma HIV-1 RNA level and TruCount T Assay

- Frequency of testing: At SV, T1, T2, T4, T6, T8, T10, T12, T14, T16 and T17, at least once every four weeks between T18-21, T22-25, T26-29, T30-33, T34-37, T38-41, T42-45, T48 and at VF visits when subject comes to clinic. In addition, blood sample will also be collected at all Virologic Failure Follow-up (VF-FU) Visits or Non-Virologic Failure Follow-up (NVF-FU) Visits.
- To assess antiretroviral therapeutic response to PRO 140 or cART regimen

**Note:** Plasma HIV-1 RNA level will be measured using Human Immunodeficiency Virus 1 (HIV-1), Quantitative, RNA (Taqman® Real-Time PCR) test.

TruCount T Assay includes measurement of Absolute Lymphocytes, CD3 cell count, CD4 cell count, CD8 cell count, CD3%, CD4% and CD8%

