#### **8.7.4 Efficacy Analysis**

All data from the primary and secondary outcome measures will be summarized and tabulated according to the variable type:

- Time to event data will be depicted using Kaplan-Meier plots
- Continuous data summaries will include number of observations, mean, standard deviation, median, and minimum and maximum values.
- Categorical data summaries will include frequency counts and percentages.

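### The SAP's rescue re-suppression measures set no ART condition, so an HIV-1 RNA below 50 at T48, after ART has restarted, can be credited to the higher PRO 140 dose

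*Protocol*

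**What the plan says.** **When ART restarts.** Protocol 4.2 (after Table 4-6), like the synopsis, states: "All study subjects will re-initiate their previous antiretroviral regimen or an alternative regimen selected by their treating physician". The first occasion it gives is "One week prior to the end of 48-week Treatment Phase, or"; the second is virologic failure or another discontinuation criterion. Table 4-2 footnote 9 has "1) One week prior to the end of 48-week Treatment Phase, or (2) Anytime during the Treatment Extension Phase, if virologic failure occurs". Section 4.2.3 has "Re-initiate previous antiretroviral regimen or an alternative regimen selected by the treating physician at Week-47, if viral load remain suppressed". The synopsis (Trial Design), Section 3 and Section 7.5.1 describe "also one week overlap at the end of the treatment in subjects who do not experience virologic failure". Section 3 attaches that overlap to Part 1. Section 7.5.1 goes on to permit ART during the Treatment Phase once failure has occurred.

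**How long Part 2 lasts.** The Note in Protocol 4.2, with matching text in 4.3 and 5.2.1, gives the higher dose as a "weekly injection for remainder of 48-week Treatment Phase or until subsequent virologic failure event after viral re-suppression on higher dose". The synopsis (Groups A and B) and the text before Table 4-6 (Group B) say instead that a further failure in Part 2 leads to the VF Visit and Follow-up. They do not require re-suppression first.

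**Sampling.** Section 4 runs the Treatment Phase from T1 to T48. Section 7.10.9 ends its RNA schedule with "T34-37, T38-41, T42-45, T48 and at VF visits when subject comes to clinic". Nothing is scheduled at T46 or T47.

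**Analysis.** SAP 7.5.6 defines re-suppression as an RNA below 50 after failure, and 7.5.7 dates it by the first such value. SAP 8.2.2.4 and 8.2.2.5 apply this within the Treatment Phase to everyone who moved to a higher dose. None of these mentions ART. SAP 7.5.8 defines a separate time from ART re-initiation for the Follow-up Phase measure in 8.2.2.7, but it removes nothing from 8.2.2.4.

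**The concern.** The proportion re-suppressed on the higher dose, and the time to it, are listed primary efficacy measures (Protocol 8.2.2, SAP 3.1.2). They are the trial's direct evidence on whether dose escalation rescues a failing subject. If a Part 2 subject restarts ART shortly before the T48 sample and first falls below 50 at T48, that value cannot be attributed to PRO 140. The SAP would still count it. The 48-week RNA summary in 8.2.2.8, where it pools assigned and rescue dosing, uses the same T48 sample and has the same weakness.

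**Working it through.** No sample-size or power figure bears on this point, so there is no stated number to reproduce. The check compares the rules and counts visits.

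**1. The restart rule for Part 2.** The only statements covering everyone are in the synopsis, Protocol 4.2 and footnote 9. Section 4.2.3 covers subjects whose viral load is suppressed and is silent on the rest. The end-overlap sentences cover subjects without failure, and every Part 2 subject has failed. Section 7.5.1 then separately allows ART after failure. A site could reasonably restart an unsuppressed Part 2 subject at Week 47, or not.

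**2. Timing.** Visit Tk falls on day 1 + 7(k − 1). T47 is day 1 + 7 × 46 = 323, and T48 is day 1 + 7 × 47 = 330.
- Restart at T47: the T48 RNA follows by 330 − 323 = 7 days, or 4 to 10 days with the ±3-day window.
- Forty-eight full weeks from T1 end on day 1 + 48 × 7 = 337. One week earlier is day 330, which is T48 itself, and there is then no post-restart sample in the Treatment Phase.
- Section 4.2.3 names Week 47. The ART row of Table 4-2, although its columns are broken in the text available, appears to begin one column before T48. Both point to T47 without settling it.

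**3. Who can reach T47 unsuppressed.** Failure requires two consecutive values of at least 200. A subject at 50–199 never meets it. The Section 7.10.9 schedule leaves these RNA samples after confirmed failure and before T48:

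| Failure confirmed at | Samples before T48 |
|---|---|
| T4 | 14 |
| T10 | 11 |
| T16 | 8 |
| T22-25 | 5 |
| T34-37 | 2 |
| T38-41 | 1 |
| T42-45 | 0 |

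With one sample or none, two new values of at least 200 cannot be obtained on schedule before T48. Subjects who enter Part 2 after failure at T38-45 are therefore also exposed. Persistently viremic earlier entrants are exposed only if the Note in 4.2 (and 4.3, 5.2.1) is followed rather than the synopsis and the text before Table 4-6.

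**4. Could RNA cross 50 in that interval?** From 60, 100 or 199 copies/mL the value must fall by a factor of more than 60/50 = 1.2, 100/50 = 2.0 or 199/50 = 3.98. Assume an RNA half-life on ART of 1, 2 or 4 days (not given in the documents). The fall over 7 days, 2^(7/half-life), is then 128-, 11.3- or 3.4-fold. Only the 199-copy subject with the 4-day half-life would remain above 50.

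**5. Size.** Let r be the true re-suppression rate on the higher dose, and x the share of the other Part 2 subjects who restart ART and first fall below 50 at T48. The reported rate is r + (1 − r)x, a rise of (1 − r)x. Both r and x are assumed.

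| x | r = 30% | r = 50% | r = 70% |
|---|---|---|---|
| 0 | 0 | 0 | 0 |
| 10% | +7 points | +5 points | +3 points |
| 25% | +17.5 points | +12.5 points | +7.5 points |

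The rise is never negative. The direction for time to re-suppression is not fixed. By the SAP 7.5.7 formula, a miscounted subject with failure at T45 (day 309) adds 330 − 309 + 1 = 22 days. One with failure at T4 (day 22) adds 330 − 22 + 1 = 309 days.

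**6. Cross-references.** SAP 8.2.2.1, 8.2.2.2, 8.2.2.4, 8.2.2.5, 8.2.2.6 and 8.2.2.7 cite 7.5.6, 7.5.7, 7.5.8, 7.5.9, 7.5.8 and 7.5.10. The matching definitions are 7.5.4, 7.5.5, 7.5.6, 7.5.7, 7.5.6 and 7.5.8, a shift of two throughout; 7.5.9 and 7.5.10 do not exist. Read literally, 8.2.2.4 points to the after-ART section.

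**The case against.** A reader might infer that the protocol sets three competing ART rules for Part 2. It does not: Section 3 ties the overlap to Part 1, Section 4.2.3 says nothing about unsuppressed subjects, and Section 7.5.1 allows ART after failure. This is an unclear rule. For the same reason, following 7.5.1 would not by itself keep ART out of Part 2.

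A reader might also infer that every viremic Part 2 subject is carried to Week 47. Under the synopsis and the text before Table 4-6, a second failure ends treatment, so persistently viremic subjects with enough samples leave earlier. That narrows the exposed group but leaves low-level viremia and late entry. The Note in 4.2 also allows extra RNA draws at the Investigator's discretion, so a late entrant may have a usable sample before the restart, although none is scheduled for failure confirmed at T42-45.

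The timing objection stands in part: counted from T1, the restart can coincide with T48 and the miscount disappears. The remaining objection is that nothing is tested (SAP 7.3, 7.4) and ART restarts are summarised and listed (SAP 8.1.5), so affected subjects can be traced. That lowers the severity. It does not repair the measure, because its definition ignores those data.

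**Conclusion.** The point holds in a limited form. As written, the SAP can credit an ART effect to the rescue dose in a listed primary efficacy measure, provided that ART is restarted at T47 in a Part 2 subject not yet below 50. The proportion can then only be raised. The documents fix neither the number of Part 2 subjects nor r nor x, so the tabulated rises show how the error behaves and do not estimate it. They give no support for claiming a large inflation, and x = 25% would be hard to reach if second failures end Part 2. Severity is minor to moderate: the summary is descriptive and confined to the rescue subset, and the cases are traceable.

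**What to change.** - **Protocol.** State one end-of-treatment ART rule for Part 2, including the day of restart, in the synopsis, Sections 3, 4.2, 4.2.3 and 7.5.1, and Table 4-2 footnote 9. The restart itself may stay, to avoid a treatment gap.
- **SAP 8.2.2.4, 8.2.2.5 and the rescue part of the 48-week summary in 8.2.2.8.** Count an RNA below 50 only on samples taken after the first higher dose and before any ART restart. Alternatively, draw the T48 efficacy RNA before the restart. Without that change, 8.2.2.8 must say which earlier sample represents Week 48.
- **No countable sample.** Report these subjects as a separate not-evaluable category and show the proportion with and without them. Calling them not re-suppressed would build in a downward error and sit badly with the no-imputation rule in SAP 7.3.
- **Time to event.** Protocol 8.7.4 says "Time to event data will be depicted using Kaplan-Meier plots". Censor any such display of rescue re-suppression at ART start.
- **References.** Correct all the shifted 7.5.x citations in SAP 8.2.2.1 to 8.2.2.7.

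The cost is mainly wording: ART and dosing data are already collected (Protocol 7.5, SAP 8.1.5 and 8.1.6), and only the alternative changes when a sample is drawn. The reported rescue rate may be lower, and some late entrants will not be evaluable.
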